9.3. Efficacy Analysis

The Full Analysis Set (FAS) will include all subjects who were randomized to the sub-study and received at least one dose of the sub-study drug (tofacitinib, MTX or placebo). The primary efficacy population for this study is defined by the FAS.

Continuous endpoints for which change or percent change from baseline is the measure to be analyzed, would require that a subject have a baseline value and at least one post-baseline value to be included in the FAS for that endpoint.

For all the efficacy and PRO endpoint analyses, the baseline will be the latest value obtained prior to the first dose of the sub-study.

Continuous endpoints collected over multiple visits (eg, Δ HAQ-DI or Δ PASDAS) will be analyzed using a Mixed Model for Repeated Measures (MMRM) without imputation for missing values on the FAS. Treatment comparison between the 2 groups at each post-baseline time point will be generated from this model providing both 2-sided p-value and 95% CI.

Binary endpoints (eg, MDA response) will be analyzed using the normal approximation for the difference in binomial proportions with missing response as non-response (MR=NR) on the FAS. Treatment comparison between the 2 groups at each post-baseline time point will be generated providing both 2-sided p-value and 95% CI.

Efficacy will also be assessed for a subset of the subjects who had more severe PsA as defined by ≥ 5 swollen or tender joints at the baseline of the sub-study, if sample size permits.

Complete details will be specified in the SAP.

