9.3.2. Analysis of Secondary and Other Endpoints

Each of the continuous secondary or other efficacy/PRO endpoints listed in [Sections 2.2.2](#) and [2.2.3](#) of the sub-study will be analyzed using a MMRM without imputation for missing values on the FAS.

Each of the binary secondary or other efficacy/PRO endpoints listed in [Sections 2.2.2](#) and [2.2.3](#) of the sub-study will be analyzed using the normal approximation for the difference in binomial proportions with missing values handled by MR=NR on the FAS.

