7. HANDLING OF MISSING VALUES

For the SF-36v2, ASQOL, DLQL, EQ-5D-3L, BASDAI, WLQ, PsA-HCRU, and FACIT-F instruments, rules suggested by the developers of these will be followed in calculating scores when individual question/items may be missing. If these rules are not enough for calculating a score, then the endpoint will be considered to have a missing value. Missing values in any of the endpoints will not be imputed when summarizing these endpoints using descriptive statistics. See [Appendix 2](#) for additional details for the calculation of endpoints, including handling of missing item values in the calculation.

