8.1.2. Analyses for Categorical Data

The data for all categorical endpoints (including binary) will be summarized by contingency tables that show the counts/frequency in the various categories at each time point. For some categorical endpoints, such as the presence or severity of adverse events, contingency or frequency tables will consider the data over the entire duration of the study and will not be constructed at each time point.

Normal approximation will be used for the construction of confidence interval (CI) for the responder rate over time. Let N be number of subjects assessed at each visit and n be number of responders, and $p_{\text{obs}} = n/N$ be the observed responder rate, then the two-sided 95% CI will be formed by $p_{\text{obs}} \pm 1.96 \times \text{squared root of } [p_{\text{obs}} \times (1 - p_{\text{obs}}) / N]$.

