1.1. Study Design

This sub-study within Study A3921092 is a Phase 3, randomized, double-blind, placebo-controlled, parallel group estimation study designed to assess the efficacy, safety and tolerability of tofacitinib 5 mg BID versus tofacitinib 5 mg BID in combination with concomitant MTX in subjects with active PsA. Subjects with active PsA will have previously completed at least 24 months of treatment with tofacitinib in Study A3921092 and will be on a stable dose of tofacitinib 5 mg BID for at least 3 months prior to the first dose of sub-study drug and be on a stable dose of oral MTX at least 4 weeks prior to the first dose of sub-study drug. For subjects who are qualified to enter into the sub-study, the Combined A3921092 Sub-study Switch/Baseline visit will occur at a scheduled study visit at or after Month 24 of A3921092. There will be no separate Baseline visit for the sub-study. The visit window will remain as in the LTE in which a month is considered 28 days. Once a subject enters the sub-study, they will complete their participation in the sub-study portion and be unable to re-enter the main study. Subjects may be discontinued from the sub-study at any time during the sub-study in the event of deterioration of response as determined by the investigator.

Eligible subjects from study A3921092, will be randomized into A3921092 sub-study in a 1:1 ratio to tofacitinib 5 mg BID + MTX placebo or tofacitinib 5 mg BID + MTX. MTX will be blinded to the subjects, investigator and the sponsor. The subjects in the tofacitinib 5 mg BID + MTX group will receive blinded MTX capsules (range dose of 7.5-20 mg a week based upon the pre-existing dose) and the subjects in the tofacitinib 5 mg BID group will receive the matching MTX placebo capsules. For the duration of the sub-study tofacitinib dose must remain stable at 5 mg BID. The MTX dose and oral route of administration must remain stable for the 12 month duration of the sub-study. All subjects will receive open-label tofacitinib 5 mg BID throughout the sub-study without dose increase. The total number of subjects randomized will be approximately 180 with 90 in each treatment group. Treatment duration for subjects participating in this sub-study is approximately 12 months.

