6. HANDLING OF MISSING VALUES

For the SF-36v2, EQ-5D-3L and FACIT-F instruments, the same approaches as for the main LTE study will be followed. Refer to main LTE study [Section 7](#) for the details. In general, missing values will not be imputed. For the binary efficacy endpoints (eg, PsARC Response), missing responses will be treated as non-response (MR=NR).

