7.1.2. Analyses for Categorical Data

The data for all categorical endpoints (including binary) will be summarized by contingency tables that show the counts/frequency of the response at each visit by treatment group. For some categorical endpoints, such as the presence or severity of adverse events, contingency or frequency tables will consider the data over the entire duration of the study and will not be constructed at each time point.

Two-sided p-value and 95% CI will be generated by normal approximation to the binomial distribution approach for the treatment comparison between the 2 groups. Let N be number of subjects assessed at each visit, n be number of responders, and $\hat{p} = n/N$ be the observed responder rate. Use subscript t to refer to the treatment group (Tofacitinib + Placebo) and c to refer to the treatment group (Tofacitinib + MTX). Then the normal approximation to the 2-sided p-value will be calculated as

$$2Pr\left\{Z \geq \left| \frac{\hat{p}_t - \hat{p}_c}{\sqrt{\frac{\hat{p}_t(1-\hat{p}_t)}{N_t} + \frac{\hat{p}_c(1-\hat{p}_c)}{N_c}}} \right| \right\},$$

where Z is Normal (0, 1) distributed.

Two-sided 95% CI will be formed by

$$(\hat{p}_t - \hat{p}_c) \pm 1.96 \sqrt{\frac{\hat{p}_t(1-\hat{p}_t)}{N_t} + \frac{\hat{p}_c(1-\hat{p}_c)}{N_c}}.$$

If there is no (ie, 0) response or 100% response in any of treatments, 0.5 will be added to the number of responses and 1 will be added to the denominator in each treatment corresponding to the pair of comparison for calculating the treatment difference, standard error, 95% CI and 2-sided p-value (Agresti, 2002).

When response rate of 0% or 100% is observed in both treatments in comparison, no formal comparison will be performed. Estimated response rate of 0% or 100% will be reported as observed.

The final results will be expressed in percentages, ie, (proportions x 100)%.

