7.2.2. Analysis of Secondary and Other Efficacy/Health Outcome Endpoints

The MMRM described in Appendix 6 [Section 7.1.1](#) will be used on FAS or endpoint specific FAS for:

- *Δ HAQ-DI score at all time points except Month 6* (see [Appendix 2.2](#)). Note that this will be accomplished by the same MMRM analysis in Appendix 6 [Section 7.2.1](#).
- *Δ PASDAS at all time points except Month 6*. Note that this will be accomplished by the same MMRM analysis in Appendix 6 [Section 7.2.1](#).
- *Δ PGA-PsO at all time points* (see [Appendix 2.11](#)).
- *% Δ BSA at all time points* (see [Appendix 2.10](#)).
- *Δ DSS at all time points*.
- *Δ in Enthesitis score (using LEI) at all time points*.
- *Δ in ACR components (tender/painful joint count (68), swollen joint count (66), Physician's Global Assessment of Arthritis, Patient's Global Assessment of Arthritis, Patient's Assessment of Arthritis Pain, CRP) at all time points* (see [Appendix 2.1](#)).
- *Physical function/other patient reported outcomes to be assessed at all time points: Δ Short-Form 36 (version 2, Acute) (see [Appendix 2.17](#)); Δ FACIT-F (see [Appendix 2.16](#)); Δ EQ5D (see [Appendix 2.15](#)); EQ-VAS.*

- Δ DAS28-3 (CRP) at all time points (see [Appendix 2.3](#)).
- Δ PGJS-VAS at all time points.

The analysis methods described in Appendix 6 [Section 7.1.2](#) will be used on the FAS or endpoint specific FAS for:

- PsARC response at all time points (see [Appendix 2.4](#)).
- Dactylitis absence at all time points.
- Enthesitis absence (using LEI) at all time points.
- MDA response at all time points.
- MDA component (yes/no) response at all time points.

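### The sub-study's binary-endpoint formula counts only subjects assessed at each visit, while the Protocol and the SAP's own missing-data section require missing = non-response on the FAS

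*SAP*

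**What the plan says.** SAP Appendix 6 Section 7.1.2 states the denominator for sub-study binary comparisons: "Let N be number of subjects assessed at each visit, n be number of responders". It calls n/N the observed responder rate and carries the same N into the p-value and the 95% CI. Section 7.2.2 sends PsARC response, dactylitis absence, enthesitis absence, MDA and the MDA components to this method, which "will be used on the FAS or endpoint specific FAS for" those endpoints.

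The missing-data rule is stated in three places:

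- SAP Appendix 6 Section 6, with PsARC as its example: "missing responses will be treated as non-response (MR=NR").
- Protocol Appendix 10 Section 9.3, binary endpoints: "with missing response as non-response (MR=NR) on the FAS".
- Protocol Appendix 10 Section 9.3.2, binary secondary and other endpoints: "with missing values handled by MR=NR on the FAS".

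Membership of the sub-study FAS (SAP Appendix 6 Section 4.1) needs randomization and one dose of sub-study drug. It does not need an assessment at the visit.

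The main extension study's Section 8.1.2 has nearly the same sentence: "Let N be number of subjects assessed at each visit and n be number of responders". It fits there, because SAP Section 7 says: "Missing values in any of the endpoints will not be imputed when summarizing these endpoints using descriptive statistics".

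**The concern.** The formula describes an observed-case analysis and the missing-data rule describes a different one. The likely origin is that the extension study's definition of N was carried into the sub-study and not adapted when the missing-data rule changed. No other section redefines N.

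The denominator matters in this design because a subject may be "discontinued from the sub-study at any time during the sub-study in the event of deterioration of response". Missingness can therefore depend on outcome, and when methotrexate is withdrawn from one arm it may differ between arms. The Early Termination visit (Protocol Appendix 10 Section 6.2.3) is used in its own window (SAP Appendix 6 Section 7.4), so the failure is counted once. In every later window that subject drops out of the denominator as written, but stays in as a non-responder under the stated rule.

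No formal decision depends on these endpoints. The sub-study has no hypotheses or decision rules (SAP Appendix 6 Sections 3.1 and 3.2). It is an estimation study, however, so estimates and intervals are what it reports, and nominal significance is claimed at p ≤ 0.05 (Protocol Appendix 10 Section 9.1).

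**Working it through.** **Inputs from the documents.** 90 subjects per arm (Protocol Appendix 10 Section 9.1) and the unpooled normal approximation (SAP Appendix 6 Section 7.1.2). All response and missingness counts below are assumptions, because the documents give none.

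**The plan's own figures.** No sizing figure is given for a binary endpoint. The two stated half-widths reproduce and are not affected: 1.96 × 0.6 × √(2/90) = 0.175 (stated 0.18) for HAQ-DI, and 1.96 × 1.6 × √(2/90) = 0.467 (stated 0.47) for PASDAS.

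**Formula.** With t the methotrexate-withdrawal arm and c the methotrexate arm, difference = n_t/N_t − n_c/N_c, and the 95% CI adds ±1.96 × √[p_t(1−p_t)/N_t + p_c(1−p_c)/N_c]. It is computed once with N = subjects assessed and once with N = FAS. If p is the rate among those assessed and m the share missing, the FAS rate is p(1−m). The difference as written minus the difference under missing = non-response is therefore p_t·m_t − p_c·m_c. It vanishes when nothing is missing or when these products are equal.

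**Single-visit cases (withdrawal v methotrexate).**

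| Case | As written | Missing = non-response |
|---|---|---|
| (a) Equal missingness and rates | 49/81 v 49/81: 60.5% each, difference 0.0 | 49/90 v 49/90: 54.4% each, difference 0.0 |
| (b) 20% missing in both arms, unequal rates | 36/72 v 45/72: -12.5 | 36/90 v 45/90: -10.0 |
| (c) 20% v 10% missing | 36/72 v 40/81: +0.6 (-15.3 to 16.5) | 36/90 v 40/90: -4.4 (-18.9 to 10.0) |
| Endpoint-specific set, 30 per arm assumed, 20% v 10% missing | 12/24 v 13/27: +1.9 | 12/30 v 13/30: -3.3 |

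Differences are in percentage points. These cases describe a visit at which the missing subjects have no assessment in that window.

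**(d) Staggered discontinuation, allowing for the Early Termination visit.** Assume 16 v 8 failures are discontinued, 4 v 2 in each of the Month 1, 3, 6 and 9 windows, with 36 v 40 responders throughout. Each discontinued subject is assessed in the termination window and missing only afterwards. Under missing = non-response, every visit gives 36/90 − 40/90 = -4.4.

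| Visit | N as written | Difference as written | Shift |
|---|---|---|---|
| Month 1 | 90 v 90 | -4.4 | 0.0 |
| Month 3 | 86 v 88 | -3.6 | 0.9 |
| Month 6 | 82 v 86 | -2.6 | 1.8 |
| Month 9 | 78 v 84 | -1.5 | 3.0 |
| Month 12 | 74 v 82 | -0.1 | 4.3 |

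Shifts are computed before rounding. The number of responders never changes; the apparent narrowing comes only from failures leaving the denominator.

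**The case against.** The strongest reply is that the SAP already chose the right rule. Section 6 of Appendix 6 governs missing values and is explicit, and Section 7.2.2 applies the method on the FAS. If the missing-data rule is applied first, every FAS subject has a response status at each visit and N becomes the FAS. On that reading, Section 7.1.2 merely has a badly chosen word.

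The intent is indeed clear, and that supports the correction. But the reading fits poorly with a denominator of subjects assessed and a quantity called the observed responder rate, and almost the same sentence in the extension study goes with no imputation. Section 7.1.2 is also the only place where the denominator is written as a formula, so it is the text a programmer is likely to code from.

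The points about weight stand. Under the discontinuation mechanism modelled in case (d), the difference never changes sign, and its largest shift (4.3 points) is under a third of the 95% CI half-width, about 14 to 16 points. The sign changes in case (c) and the 30-per-arm case need subjects missing at the visit with nearly equal response among those assessed, and do not model capture of failures in the termination window. No example crosses p = 0.05; the largest difference, case (b), gives p of about 0.13 as written and 0.18 under missing = non-response. The 2:1 missingness ratio is assumed. The sub-study's precision was set for the two primary endpoints, which are analysed by mixed model.

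**Conclusion.** The concern holds. As written, the denominator contradicts both the SAP's own missing-data section and the Protocol, and nothing elsewhere resolves it. It is a wrong rule in the formula, not a missing detail.

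The consequence is moderate: inflated responder rates in both arms wherever responses are missing, and a shift in the treatment difference of p_t·m_t − p_c·m_c. Under the assumed counts, the shift ranges from nothing (case a, and Month 1 of case d) to about 5 points (case c and the 30-per-arm case). It is confined to secondary and other binary endpoints with no formal decision attached. It should be corrected because it acts on the by-visit comparison when discontinuation for deterioration differs between arms.

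**What to change.** In SAP Appendix 6 Section 7.1.2, define N as the number of subjects in that arm's FAS, or in the endpoint-specific FAS of Table 3 where one applies, with a missing response at a visit counted as non-response. Drop the description of n/N as observed. If an observed-case table is also wanted, add it and label it supportive. The extension study's Section 8.1.2 can stay as it is.

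The cost is one phrase in the SAP. It needs no new data and no Protocol amendment, since the Protocol already states the intended rule.

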7.2. Statistical Analyses

The primary efficacy analysis will use FAS (Appendix 6 [Section 4.1](#)). Continuous efficacy endpoints, for which change or percent change from baseline is the measure to be analyzed, would require that a subject have both a baseline value and at least one post-baseline value to be included in the FAS. The safety analysis will use SAS (Appendix 6 [Section 4.3](#)).

7.2.1. Analysis of Primary Endpoints

For each of the two primary endpoints in the sub-study: Δ HAQ-DI at Month 6 and Δ PASDAS at Month 6, a MMRM described in Appendix 6 [Section 7.1.1](#) on the FAS without imputation for missing values will be used to estimate the change from baseline at Month 6 for each treatment group. The treatment comparison between the 2 groups at Month 6 will also be generated from this model providing both 2-sided p-value and 95% CI. The analysis will include all the data through Month 12. Treatment comparisons between the 2 treatment groups at other visits will be made as well from this model.

7.2.2. Analysis of Secondary and Other Efficacy/Health Outcome Endpoints

The MMRM described in Appendix 6 [Section 7.1.1](#) will be used on FAS or endpoint specific FAS for:

- *Δ HAQ-DI score at all time points except Month 6* (see [Appendix 2.2](#)). Note that this will be accomplished by the same MMRM analysis in Appendix 6 [Section 7.2.1](#).
- *Δ PASDAS at all time points except Month 6*. Note that this will be accomplished by the same MMRM analysis in Appendix 6 [Section 7.2.1](#).
- *Δ PGA-PsO at all time points* (see [Appendix 2.11](#)).
- *% Δ BSA at all time points* (see [Appendix 2.10](#)).
- *Δ DSS at all time points*.
- *Δ in Enthesitis score (using LEI) at all time points*.
- *Δ in ACR components (tender/painful joint count (68), swollen joint count (66), Physician's Global Assessment of Arthritis, Patient's Global Assessment of Arthritis, Patient's Assessment of Arthritis Pain, CRP) at all time points* (see [Appendix 2.1](#)).
- *Physical function/other patient reported outcomes to be assessed at all time points: Δ Short-Form 36 (version 2, Acute) (see [Appendix 2.17](#)); Δ FACIT-F (see [Appendix 2.16](#)); Δ EQ5D (see [Appendix 2.15](#)); EQ-VAS.*

- Δ DAS28-3 (CRP) at all time points (see [Appendix 2.3](#)).
- Δ PGJS-VAS at all time points.

The analysis methods described in Appendix 6 [Section 7.1.2](#) will be used on the FAS or endpoint specific FAS for:

- PsARC response at all time points (see [Appendix 2.4](#)).
- Dactylitis absence at all time points.
- Enthesitis absence (using LEI) at all time points.
- MDA response at all time points.
- MDA component (yes/no) response at all time points.

7.2.3. Analysis of Safety Data

- Safety analysis by treatment groups will follow the similar approaches as for the main LTE study, except the incidence rate analysis will not be performed in the sub-study. Refer to main LTE study [Section 8.2.1](#) Analysis of Primary Endpoints and [Section 8.2.3](#) Analysis of Safety Data for the details.

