2.1.2. Secondary Objective

- To assess the safety and tolerability of tofacitinib 5 mg BID monotherapy as compared to tofacitinib 5 mg BID with background MTX in subjects who had received prior treatment of tofacitinib in combination with MTX.

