3. SUB-STUDY DESIGN

This sub-study within Study A3921092 is a Phase 3, randomized, double-blind, placebo-controlled, parallel group estimation study designed to assess the efficacy, safety and tolerability of tofacitinib 5 mg BID versus tofacitinib 5 mg BID in combination with concomitant MTX in subjects with active PsA. Subjects with active PsA will have previously completed at least 24 months of treatment with tofacitinib in Study A3921092 and will be on a stable dose of tofacitinib 5 mg BID for at least 3 months prior to the first dose of sub-study drug and be on a stable dose of oral MTX at least 4 weeks prior to the first dose of sub-study drug. This sub-study will be referred to as A3921092 Sub-study. For subjects who are

qualified to enter into the sub-study, the Combined A3921092 Sub-study Switch/Baseline visit will occur at a scheduled study visit at or after Month 24 of A3921092. There will be no separate Baseline visit for the sub-study. The visit window will remain as in the LTE in which a month is considered 28 days. Once a subject enters the sub-study, they will complete their participation in the sub-study portion and be unable to re-enter the main study. Subjects may be discontinued from the sub-study at any time during the sub-study in the event of deterioration of response as determined by the investigator.

Eligible subjects from study A3921092, will be randomized into A3921092 sub-study in a 1:1 ratio to tofacitinib 5 mg BID + MTX placebo or tofacitinib 5 mg BID + MTX. MTX will be blinded to the subjects, investigators and the sponsor. The subjects in the tofacitinib 5 mg BID + MTX group will receive blinded MTX capsules (range dose of 7.5-20 mg a week based upon the pre-existing dose) and the subjects in the tofacitinib 5 mg BID group will receive the matching MTX placebo capsules. For the duration of the sub-study tofacitinib dose must remain stable at 5 mg BID. The MTX dose and oral route of administration must remain stable for the 12 month duration of the sub-study. All subjects will receive open-label tofacitinib 5 mg BID throughout the sub-study without dose increase. The total number of subjects randomized will be approximately 180 (Sub-Study [Table 2](#)).

Sub-Study Table 2

Treatment Group	Double blind placebo controlled period	Number of Subjects
B	Tofacitinib 5 mg BID + Placebo	90
C	Tofacitinib 5 mg BID + Methotrexate	90

Treatment duration for subjects participating in this sub-study is approximately 12 months.

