8.2.1. Analysis of Primary Endpoints

Safety analysis will include cumulative data from both the main LTE study and sub-study.

- Adverse events will be summarized according to Pfizer Data Standards (PDS).
- Incidence rate (IR) defined as the number of subjects with an event in the numerator divided by the study drug exposure in the denominator (expressed as the number of subjects with an event per 100 patient-years) will be calculated for deaths, SAEs, AEs leading to discontinuation and AEs of special interest. AEs of special interest include but may not be limited in the events listed in **Table 2** AEs of Special Interest. The event will be counted from subject's first dose to subject's last dose of study drug + 28 days. The denominator is the sum of the time to event or to subject's last dose of study drug + 28 days, whichever is earlier.

Table 2 AEs of Special Interest

Serious infections (SIs)
Herpes zoster (HZ)
Adjudicated opportunistic infections (OIs) excluding tuberculosis (TB) ^a
Hematologic events (anaemia, neutropenia, lymphopenia, and thrombocytopenia)
Adjudicated malignancies ^a
Adjudicated major adverse cardiovascular events (MACE) ^{a,b}
Adjudicated drug-induced liver injury (DILI) ^a and other hepatic events ^c
Renal events ^d
Adjudicated gastrointestinal (GI) perforations ^a
Adjudicated interstitial lung disease (ILD) ^e

Abbreviations: DILI = drug-induced liver injury; GI = gastrointestinal; HZ = herpes zoster; ILD = interstitial lung disease; MACE = major adverse cardiovascular events; MedDRA = Medical Dictionary for Regulatory Activities; OI = opportunistic infection; SI = serious infection; SMQ = Standardised MedDRA Queries; TB = tuberculosis.

a. Adjudicated by Adjudication Committees independent and external to Pfizer.

b. Components: cardiovascular death, non-fatal myocardial infarction, and non-fatal stroke.

c. Including SMQs: Hepatic failure, fibrosis, and cirrhosis, and other liver damage-related conditions; and Hepatitis, non-infectious.

d. Including Acute renal failure SMQ.

e. Adjudicated by an internal review committee.

- Safety laboratory tests will be summarized according to the PDS.

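### The sub-study drops exposure-based adverse event rates, so its AE percentages could favour whichever arm leaves earlier (minor; cheap to repair)

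*SAP*

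**What the plan says.** The safety objective in Protocol Appendix 10 Section 2.1.2 is comparative: "To assess the safety and tolerability of tofacitinib 5 mg BID monotherapy as compared to tofacitinib 5 mg BID with background MTX".

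For the main study, SAP Section 8.2.1 sets out an exposure-based measure: "Incidence rate (IR) defined as the number of subjects with an event in the numerator divided by the study drug exposure in the denominator". It covers deaths, SAEs, AEs leading to discontinuation and AEs of special interest, and counts events up to 28 days after the last dose. For the sub-study, SAP Appendix 6 Section 7.2.3 applies the same safety approach by treatment group, "except the incidence rate analysis will not be performed in the sub-study". No reason is given.

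For AEs this leaves summaries under the sponsor's data standards and, in SAP Appendix 6 Section 7.1.2, tables for which "contingency or frequency tables will consider the data over the entire duration of the study and will not be constructed at each time point". Section 7.4 of the same appendix adds exposure and duration summaries for tofacitinib, and Section 7 says reporting is by treatment group. Neither links exposure to the AE counts.

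On leaving early, Protocol Appendix 10 Section 3 says: "Subjects may be discontinued from the sub-study at any time during the sub-study in the event of deterioration of response as determined by the investigator". Section 7.6.9.2 lists toxicity and rescue-use criteria that also end participation.

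**The concern.** Randomisation balances the arms at entry, not the time each arm is then observed. In the placebo arm methotrexate stops without a taper. In both arms the tofacitinib dose cannot be raised, nobody may return to the main study, and an investigator may withdraw a subject whose response worsens. If losing methotrexate matters clinically, the placebo arm may leave earlier. If methotrexate toxicity matters more, the other arm may.

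Under Protocol Section 8.2, AEs are recorded on the CRF only to the last visit, and active SAE reporting ends 28 days after the last dose. An early leaver therefore stops contributing events. A percentage with the number of subjects as denominator then mixes the event rate with the length of observation.

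No other planned analysis fills the gap. The main-study incidence rates include sub-study data, but SAP Section 8.2 presents a single flexible-dose cohort, so they give nothing by sub-study arm.

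**Working it through.** **Plan figures.** The plan states no safety figure to reproduce. Its only sizing figures (Protocol Appendix 10 Section 9.1, 90 per arm) do reproduce: 1.96 × 0.6 × √(2/90) = 0.175, stated as about 0.18 for HAQ-DI; 1.96 × 1.6 × √(2/90) = 0.467, stated as about 0.47 for PASDAS.

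**Inputs from the documents.** 90 per arm; 12 months of 28 days, so T = 336/365.25 = 0.920 years.

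**Assumed, because the documents are silent.** Dropout proportion d by arm; a constant first-event rate r, set equal in both arms; constant dropout hazard m = −ln(1 − d)/T.

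**Formulas.** Crude proportion = r/(r + m) × [1 − exp(−(r + m)T)]. Mean time on study = d/m. The incidence rate, events over time to event or exit, equals r in both arms whatever the dropout.

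**Worked case, r = 0.10 per year, dropout 20% v 5%.**
- d = 0.20: m = 0.2231/0.920 = 0.2426; 0.10/0.3426 × [1 − exp(−0.3151)] = 0.2919 × 0.2703 = 7.89%.
- d = 0.05: m = 0.0513/0.920 = 0.0558; 0.10/0.1558 × [1 − exp(−0.1433)] = 0.6420 × 0.1335 = 8.57%.
- Ratio 7.89/8.57 = 0.92, although both true rates are 10 per 100 patient-years.

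| Dropout, earlier-leaving v other arm | Mean exposure ratio | Crude %, 10 per 100 PY | Ratio | Crude %, 100 per 100 PY | Ratio |
|---|---|---|---|---|---|
| 5% v 5% | 1.00 | 8.57 v 8.57 | 1.00 | 58.9 v 58.9 | 1.00 |
| 10% v 5% | 0.97 | 8.35 v 8.57 | 0.97 | 57.5 v 58.9 | 0.98 |
| 20% v 5% | 0.92 | 7.89 v 8.57 | 0.92 | 54.8 v 58.9 | 0.93 |
| 40% v 10% | 0.83 | 6.91 v 8.35 | 0.83 | 48.9 v 57.5 | 0.85 |

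**In events.** At 2 per 100 patient-years and 40% v 10% dropout, the gap is 0.30 percentage points × 90 = 0.27 subjects. At 5 per 100 it is 0.74 points × 90 = 0.67. At 10 per 100 it is 1.44 points × 90 = 1.3.

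**Against chance.** For a common AE at 20% v 5%, the shift is 58.9 − 54.8, about 4 points. The 95% half-width for a difference near 60% is 1.96 × √(2 × 0.6 × 0.4/90) = 14 points.

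**Change of sign.** Give the earlier-leaving arm a true rate 10% higher (base 10 per 100 patient-years). The crude ratio is 1.01 at 20% v 5%, 0.97 at 30% v 10% and 0.91 at 40% v 10%.

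**Event window.** Take withdrawals of 25% and 5%, all at Month 4. Exposure fractions are 0.75 + 0.25 × 4/12 = 0.833 and 0.95 + 0.05 × 4/12 = 0.967, ratio 0.862. Adding an unobserved 28 days (1/12) to every denominator gives 0.917 and 1.050, ratio 0.873. Equal true rates would then show as 0.862/0.873 = 0.99. The error is small but avoidable.

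**The case against.** The best defence is that this is a descriptive, 1:1, fixed 12-month comparison in which little depends on the choice. Protocol Appendix 10 Section 9.4.1 summarises safety descriptively. SAP Appendix 6 Sections 3.1 and 3.2 set no hypotheses or decision rules, and Section 7.2.2 assigns the p-value and interval methods to efficacy endpoints. Unequal time on tofacitinib would be visible in the Section 7.4 tables. Laboratory change from baseline is summarised by visit, where the person-time argument does not apply in the same way. For rare events the distortion is well inside chance variation. All of this stands, and it limits the weight of the point. It does not remove the point: the exposure tables reveal an imbalance without correcting the AE comparison, and a systematic shift is not excused by random error being larger.

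A reader might infer that tofacitinib monotherapy will look safer than it is. The documents do not support that. Protocol Appendix 10 Section 1.2 says placebo-controlled trials have not clearly shown that methotrexate works in this disease, so an excess of early leavers on placebo cannot be presumed. Toxicity could shorten follow-up in the methotrexate arm instead. Nor can any one ratio above be read as the expected bias, since no dropout figure is given overall or by arm.

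**Conclusion.** The concern holds as a minor one. An exposure-adjusted comparison of the sub-study arms is planned nowhere, and the design allows time on study to depend on treatment. If it does, crude AE percentages favour the earlier-leaving arm, whichever that is.

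Under equal true rates the ratio runs from 1.00 (no dropout difference) to about 0.83 (40% v 10%). That is less than one event per arm at rates up to 5 per 100 patient-years. These values rest on assumed dropout, constant hazards and dropout unrelated to event risk. They also read the remaining AE summaries as counts and percentages, as Section 7.1.2 indicates; the sponsor's data standards, which hold the details, are not part of the documents.

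A side effect: within the SAP, the 28-day counting rule is written only in the incidence-rate text, so removing that analysis leaves the sub-study AE counting window unstated there.

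**What to change.** In SAP Appendix 6 Section 7.2.3, delete the exception. Beside the counts, report by sub-study arm the patient-years and the Section 8.2.1 incidence rates for deaths, SAEs, AEs leading to discontinuation and AEs of special interest. Start time at risk at the first sub-study dose.

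Do not carry over the 28-day window unchanged. Protocol Section 8.2 stops CRF recording at the last visit, and Appendix 10 Section 6.2.4 requires a follow-up visit only after discontinuation with qualifying laboratory abnormalities or for an AE. The window should match collection. For example, end time at risk at the event or, if sooner:
- for CRF-recorded non-serious AEs, the earlier of last dose + 28 days and last contact;
- for SAEs and deaths, last dose + 28 days.

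The cost is a few lines of SAP text and a rerun of the main-study rate calculation by arm; no new data are needed. Intervals for rare events will be wide. Rates also do not remove informative censoring, so reasons for and timing of withdrawal by arm should be read alongside them.
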